4.3.4. PK Analysis Set

The PK analysis set is a subset of the safety set for patients who have at least one baseline and post-baseline serum PK concentration result. Patients with protocol deviations, or who experience dosing or other issues which are deemed to affect the PK data, will be considered for exclusion from the PK analysis set on a case-by-case basis. Patients will be included in the dose cohort corresponding to the dose level which they actually received.

5. Patient Disposition

Patient disposition data will be summarized using the safety set by treatment arm and dose cohort of mRNA-2416 (as specified in [Section 3.3](#)), total for each treatment arm combining Phase I and Phase II, and overall of Arm A and Arm B, unless otherwise specified.

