10.13 BIOMARKERS

In this study, biomarker samples will be collected per Tables 6, 7,8 and 9. The biomarker analysis will be used to investigate the effect of mRNA-2416, as well as to determine how the markers are associated with clinical outcome. Immune responses will be studied in the peripheral circulation and in tumor biopsy specimens. Tumor biopsies will be examined using methods such as immunohistochemistry, quantitative immunofluorescence, RNA sequencing and/or electrochemiluminescence (ECL) assays to evaluate changes in key immune pathway axes, such as PD-L1/PD-1 and OX40L/OX40, as well as characterization (eg, phenotype, distribution, and activation) of tumor infiltrating lymphocyte and myeloid populations. Cytokines may also be examined in both tumor and blood tissues using methods such as RNA sequencing and enzyme-linked immunosorbent assay (ELISA)/ ECL assays, respectively.

The goal of the biomarker assessments is to provide supportive data for the clinical study; however, there may be circumstances when a decision is made to stop a collection or not perform or discontinue an assessment (eg, inadequate sample number, sample quality or assay issues that preclude analysis, or impossibility to perform correlative analyses). Therefore, sample collection and/or assessment may be omitted at the discretion of the Sponsor.

The sample collection information must be entered on the appropriate sample collection log eCRF page(s). Sample details including volume and instructions for the collection, handling, and shipment of samples are outlined in the laboratory manual for the study.

Table 6: Sampling schedule for Pharmacokinetics, Immunogenicity, and Cytokine Profiling

Cycle	Day	Scheduled Time (Sampling Window)	Purpose ^a
1	1	Pre-dose of Cycle 1 Day 1	PK, Cytokines, IG
1	1	3 h from start of injection (\pm 10 min)	PK, Cytokines
1	1	6 h from start of injection (\pm 30 min)	PK, Cytokines
1	2	24 h from start of injection (\pm 60 min)	PK, Cytokines
1	8	168 h from start of injection (\pm 24 h)	PK, Cytokines
1	15	Pre-dose of Cycle 1 Day 15	IG
2	1	Pre-dose of Cycle 2 Day 1	PK, Cytokines, IG, mAb PK
3	1	Pre-dose of Cycle 3 Day 1	IG
3	15	Pre-dose of Cycle 3 Day 15	IG
4	1	Pre-dose of Cycle 4 Day 1	IG
5	1	Pre-dose of Cycle 5 Day 1	IG
6	1	Pre-dose of Cycle 6 Day 1	IG
6	15	Pre-dose of C1D15	IG
EOT		Anytime	IG
Unscheduled		Anytime when needed	PK, Cytokines, IG, mAb PK

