Unless otherwise specified, the first/last dose refers to the first/last dose of study drug (mRNA-2416 or durvalumab). Study day for events on or after the date of the first dose will be defined as the number of days from the date of the first dose, plus 1 day, so that the date of the first dose will be defined as Day 1. For events before the date of the first dose, study day will be calculated as the difference in days between the date of the first dose and the date of interest. Thus, the day before the date of the first dose will be defined as Day -1. This means there will be no study Day 0.

Baseline is defined as the last assessment prior to the first dose. All baseline measurements must have been collected prior to administration of the first dose. Measurements obtained after the first dose will be considered as post-baseline values. If the measurement of a variable is not made on a given patient prior to the first dose, that patient will be considered not to have a baseline value for that variable. Change from baseline is defined as post-baseline assessment minus baseline assessment.

Continuous data will be described using the following descriptive statistics: the number of patients (n), mean, standard deviation, median, minimum and maximum, where appropriate. Categorical data will be summarized using the frequency count (n) and percentage (%) of patients for each category, where appropriate. Percentages will be based on non-missing data unless specified otherwise.

Unless otherwise specified, all statistical tests will be 2-sided and conducted at the 0.05 significance level.

No imputation will be applied for missing data unless otherwise specified.

All collected data used for safety and efficacy evaluations will be presented in listings. Data will be displayed in all listings sorted by treatment arm, cohort (dose escalation/confirmation/expansion), dose cohort, and patient identifier unless otherwise specified.

The Medical Dictionary for Regulatory Activities (MedDRA) will be used for coding AEs and medical histories. Prior or concomitant medication data will be coded using the World Health Organization (WHO) Drug Dictionary.

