11.1. General

The PK Analysis Set will serve as the primary analysis set for PK analyses. The analysis will be conducted by treatment arm and dose cohort of mRNA-2416 (as specified in [Section 3.3](#)) for Phase I and Phase II.

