11.2. Values Below the Limit of Quantitation or Missing

Concentration values that are below the limit of quantification (BLQ) will be set to zero, with defined exceptions as follows:

- Any embedded BLQ value (between 2 quantifiable concentrations) and BLQ values following the last quantifiable concentration in a profile will be set to missing for the purposes of PK analysis.
- If there are late positive concentration values following 2 BLQ concentration values in the apparent terminal phase, these values will be evaluated. If these values are considered to be anomalous, they will be set to missing.
- If an entire concentration-time profile is BLQ, the profile will be excluded from the PK analysis.
- If a pre-dose concentration is missing, these values may be set to zero.

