11.4. Serum Concentration

Blood samples for determination of mRNA-2416 serum concentrations and durvalumab serum concentrations will be collected via venipuncture or an indwelling catheter in Cycle 1 at pre-dose (prior study drug administration), at 3, 6 and 24 (Cycle 1 Day 2) hours post-dose and at pre-dose on Cycle 1 Day 8 and Cycle 2 Day 1.

Serum concentration data of mRNA-2416 and durvalumab will be individually listed and summarized using descriptive statistics by nominal time point (n, mean, standard deviation, coefficient of variation [CV], geometric mean, median, minimum, and maximum). Geometric mean will not be calculated where the minimal concentration values include zero.

Geometric mean serum concentration by nominal time profiles by period and treatment both in linear and semi-logarithmic scale will be provided; individual serum concentration plots by actual sampling time for all patients combined within period and treatment will be provided on a linear and semi-logarithmic scale.

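### The PK analysis set requires a baseline concentration, so one missed pre-first-dose draw excludes an otherwise usable mRNA-2416 profile, and on the plain reading the SAP's zero rule does not reach that patient

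*SAP*

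**What the plan says.** SAP 4.3.4 draws the PK analysis set from the safety set and admits "patients who have at least one baseline and post-baseline serum PK concentration result". It also allows case-by-case exclusion for deviations or dosing problems that affect the PK data. SAP 11.1 then states: "The PK Analysis Set will serve as the primary analysis set for PK analyses". Neither the SAP nor Protocol 13.4.1 defines another PK set.

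SAP Section 4 (General Statistical Considerations) says: "Baseline is defined as the last assessment prior to the first dose". If a variable was not measured before the first dose, "that patient will be considered not to have a baseline value for that variable".

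SAP 11.4 places the draws "in Cycle 1 at pre-dose (prior study drug administration), at 3, 6 and 24 (Cycle 1 Day 2) hours post-dose", followed by Cycle 1 Day 8 and Cycle 2 Day 1, both of which it labels pre-dose. Protocol Table 6 (Section 10.13) also has one PK draw ahead of first dosing, "Pre-dose of Cycle 1 Day 1". It schedules durvalumab PK only before dosing on Cycle 2 Day 1.

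SAP 11.2 begins "Concentration values that are below the limit of quantification (BLQ) will be set to zero" and lists exceptions. The last reads "If a pre-dose concentration is missing, these values may be set to zero". SAP 11.3 lets the pharmacokineticist leave pre-dose values above 5% of Cmax out of the summaries.

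**The concern.** Eligibility for every PK summary hangs on a single blood draw whose result, for mRNA-2416, is known in advance as nearly as anything in PK can be. Protocol 6.2 describes this as the first-in-human study of mRNA-2416, so the expected concentration before the first dose is zero. A patient with complete post-dose samples but no Day 1 pre-dose result is nevertheless left out.

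Cmax and AUC of mRNA-2416 are secondary endpoints (SAP 3.2.2) and are summarised by arm and dose cohort (SAP 11.1). Escalation cohorts hold 3 to 6 patients, so one avoidable exclusion there is noticeable. The zero option in 11.2 would solve the problem, but as written it seems to act only on patients already in the set.

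**Working it through.** The documents give no figure on this point to reproduce. The 3 to 6 cohort size is a 3+3 design rule, with no formal sample-size estimation (SAP 4.1). The check is therefore a reading of the rules, followed by simple arithmetic.

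**1. Who enters the set.** Take two patients with identical, complete post-dose mRNA-2416 samples.

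| Day 1 pre-dose sample | Baseline result (SAP 4)? | In PK set (4.3.4)? | Pre-dose value used |
|---|---|---|---|
| Measured, BLQ | Yes | Yes | 0 (11.2, mandatory) |
| Missing | No | No, on the plain reading | 0 would be allowed (11.2, optional), but is not reached |

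Both patients would carry the same pre-dose value, yet one is kept and the other dropped. The SAP does not say whether an imputed zero counts as a baseline result, or whether imputation comes before set membership is decided.

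**2. Which parameters need the sample (SAP 11.5).** Cmax and tmax are read from the observed data. The terminal rate constant and half-life use the terminal phase. AUC uses the pre-dose value only in its first segment. With a rise from 0 to the 3-hour concentration C3 at nominal times, the linear-up rule gives (0 + C3)/2 × 3 = 1.5 × C3. This is the same whether the zero is a measured BLQ or an imputed value.

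**3. Share lost per excluded patient = 1/n.**

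- Escalation cohort (SAP 4.1): 1/3 = 33.3%; 1/6 = 16.7%.
- Arm A level with up to 9 biopsy patients (SAP 3.1), 3 + 9 = 12 to 6 + 9 = 15: 1/12 = 8.3%; 1/15 = 6.7%.
- Phase II evaluable targets (SAP 4.1): 1/27 = 3.7%; 1/41 = 2.4%.

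**4. Chance of losing at least one patient = 1 − (1 − p)^n.** The documents do not give p, the probability that the Day 1 pre-dose result is missing. The values below are assumptions.

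| n | p = 2% | p = 5% | p = 10% |
|---|---|---|---|
| 3 | 5.9% | 14.3% | 27.1% |
| 6 | 11.4% | 26.5% | 46.9% |
| 15 | 26.1% | 53.7% | 79.4% |

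**5. Where the zero rule still operates.** It remains available for later samples labelled pre-dose. For durvalumab, Protocol 6.5 gives a half-life of about 21 days. Under simple first-order decay, the fraction left after 28 days is 2^(−28/21) = 0.40. A zero on Cycle 2 Day 1 would therefore be wrong for that drug.

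**The case against.** A reader might infer that 4.3.4 and 11.2 flatly contradict each other. They do not. The wording of 11.2 is permissive and refers to any pre-dose concentration. SAP 11.4 labels later samples pre-dose too, so a patient with a Day 1 baseline can be in the set and still need the rule. A lenient programmer could also impute first and assign membership afterwards. What stands is that the plain reading excludes the patient and the order of operations is not stated.

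A reader might also infer that a baseline requirement has no value. It has some: the 11.3 check against 5% of Cmax cannot be run without a measured pre-dose result. That is a reason to flag such patients, and 4.3.4 already has case-by-case exclusion for real problems, so a blanket exclusion is more than the check requires.

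The strongest objection concerns durvalumab. A zero before the first study dose is a sound expectation for mRNA-2416 but not for durvalumab in every patient. Exclusion criterion 19 admits prior anti-PD-L1 therapy under conditions, and criterion 2 asks for 28 days since an anti-cancer antibody. Prior durvalumab is not expressly excluded. By the half-life calculation above, about 40% of a concentration could remain at 28 days. This objection stands in full and limits the remedy to mRNA-2416.

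Finally, PK output is descriptive, and Protocol 13.4.4 lists individual mRNA-2416 concentrations without tying the listing to a PK set. An excluded patient's data may therefore still be visible, though outside the summaries.

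**Conclusion.** The point holds in a limited form. As written, SAP 4.3.4 can remove a usable mRNA-2416 profile from the primary PK set because of one missing sample whose expected value is zero, while the zero option stays open at later times when it is harder to justify. The relative loss per patient is 33% to 17% in a bare escalation cohort, about 8% to 7% in a fully enriched Arm A level, and 4% to 2% at the Phase II targets.

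The documents do not show that any profile has been or will be lost. That depends on a missing-sample rate they do not state. The conclusion rests on the plain reading of baseline result and on a true zero before the first dose of mRNA-2416. The MTD rests on DLTs and the Phase II decision on response counts, so neither is affected. This is a minor improvement to descriptive secondary PK summaries.

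A reader might go further and conclude that no patient could have a durvalumab profile analysed, because Table 6 has no durvalumab draw before the first dose. The documents do not settle that: 4.3.4 names no analyte, and SAP 11.4 lists a Cycle 1 pre-dose sample for both drugs. It is a further reason to define the set by analyte.

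**What to change.** Replace the entry rule in SAP 4.3.4 with a per-analyte one: safety-set patients with at least one post-dose concentration result for that analyte, quantifiable or BLQ. Keep the existing case-by-case exclusions and the 11.2 exclusion of profiles that are entirely BLQ.

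In SAP 11.2, limit the zero rule to a missing Cycle 1 Day 1 pre-dose value of mRNA-2416 and flag that value in the listing. Leave later missing pre-dose values missing. Do not assume zero for durvalumab in patients with possible prior durvalumab exposure.

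The cost is a few sentences of SAP text and one listing flag, with no new data collection. The one real downside is that the 11.3 check against 5% of Cmax cannot be done for the flagged patients.

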5.1. Disposition

A summary of analysis sets will be presented for the ITT set, the safety set, the activity evaluable set, and PK analysis set. Analysis set will also be presented in a listing using the ITT set.

The patient disposition summary will present the number and percentage of patients for the following categories:

- End of treatment: patients who received mRNA-2416, patients who completed mRNA-2416, patients who discontinued mRNA-2416, the reasons for discontinuation of mRNA-2416, patients who received durvalumab, patients who completed durvalumab, patients who discontinued durvalumab, and the reasons for discontinuation of durvalumab.
- End of study: patients who completed the follow-up period, patients who discontinued from the follow-up period, and the reasons for discontinuation of the follow-up period.

The reasons for discontinuation of mRNA-2416 will be summarized based on the following categories:

- Adverse event
- Patient no longer has lesions that meet injection criteria
- Pregnancy
- Investigator decision
- Withdrawal of consent
- Death
- Disease progression
- Symptomatic deterioration/clinical progression
- Non-compliance
- Receiving alternate anticancer therapy
- Other

The reasons for discontinuation of durvalumab will be summarized based on the following categories:

- Adverse event
- Pregnancy
- Investigator decision
- Withdrawal of consent
- Death
- Disease progression
- Symptomatic deterioration/clinical progression
- Non-compliance
- Receiving alternate anticancer therapy
- Completed 2 years of durvalumab treatment
- Other

Patients who completed 6 cycles of durvalumab treatment are considered for completion of durvalumab treatment. Patients who discontinued durvalumab treatment after completing 6 cycles of durvalumab treatment are not considered for discontinuation of durvalumab treatment.

The reasons for discontinuation from the follow-up period will be summarized based on the following categories:

- Withdrawal of consent

- Patient received alternate anti-cancer therapy
- Death
- Lost to follow up
- Other

All patient disposition data will be provided in the listings.

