8.3 STUDY FLOW AND EXPECTED DURATION OF PATIENT PARTICIPATION

All patients will participate in a Screening Phase, Treatment Phase, and Follow-up Phase.

Screening Phase:

- A 14-day screening period before enrollment (\leq 28 days for baseline biopsy and imaging)
- Patients will be evaluated against study inclusion and exclusion criteria. Patients must meet all inclusion criteria and none of the exclusion criteria at screening in order to be eligible for the study. Assessments required on C1D1 that are performed as part of the screening evaluations and within 72 hours prior to the first dose of study treatment, do not need to be repeated on C1D1.

Treatment Phase:

- Arm A: mRNA-2416 administered for 6 cycles
- Arm B: Combination dosing of mRNA-2416 with durvalumab for 6 cycles. Following completion of 6 cycles of combination dosing, patients may continue with durvalumab as a single-agent until disease progression, unacceptable toxicity, or 24 months of treatment (total), whichever is sooner.

Safety Follow-up:

- Patients will be followed up for safety evaluation 30 and 90 days after their last dose of study treatment.

Disease Progression Follow-up:

Patients who complete study treatment with an overall tumor assessment of stable disease (SD) or better will be followed for tumor assessment 60 and 180 days after their last dose of study treatment, or until disease progression, whichever occurs first.

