10.5 Dose Omissions and Discontinuation of Study Drug Administration

Study treatment may be interrupted for situations other than treatment-related AEs such as medical and/or surgical events or logistical reasons not related to study treatment. Patients should be placed back on study

treatment within 3 weeks of the scheduled interruption, unless otherwise discussed with the Sponsor. The reason for interruption should be documented in the patient's study record.

Patients who have permanently discontinued study therapy will be scheduled for an End of Treatment visit within 14 days (± 2 days) of the decision to permanently discontinue study therapy and assessments will be performed per the Schedule of Events table ([Section 3](#)). Patients who have permanently discontinued study therapy should not be considered withdrawn from the study. They should return for the 30-day and 90-day safety follow-up visit from last dose and the tumor assessment follow-up visits per the Schedule of Events table. If the patient fails to return for these assessments for unknown reasons, every effort (e.g. telephone, email, letter) should be made to contact them.

The following are reasons for discontinuing study therapy without necessarily requiring withdrawal from the study:

- Patients who have completed 6 cycles of study therapy and have an overall tumor assessment of SD or better
- Patients who have experienced a Grade 4 treatment-related AE at any time during study treatment must discontinue from study treatment
- Patients who, in the opinion of the investigator, have incurred a Grade 3 drug-related DLT that has not recovered to Grade 1 or less within 14 days, or has recurred following restarting study therapy at a modified dose level.
- Patients who, in the opinion of the investigator, have incurred unacceptable toxicity that does not meet the pre-determined criteria for DLT (eg, late-onset, treatment-emergent toxicity after the DLT assessment window, or Grade 2 toxicities that are sufficiently durable or unresponsive to supportive intervention as to render them unacceptable in the opinion of the investigator) which has not recovered to Grade 1 or less within 28 days, or has recurred following restarting study therapy at a modified dose level.
- Patients who experience a Grade 3 hypersensitivity reaction or autoimmune events must discontinue from study treatment
- Patients who no longer have lesions that meet criteria for injection
- Pregnancy
- Physician's decision

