3.1. Overall Study Design and Plan

This is an open-label, multicenter, Phase I/II Dose Escalation study of repeated intratumoral injections of mRNA-2416 alone (Arm A) and in combination with intravenously administered durvalumab (Arm B) in patients with advanced relapsed/refractory solid tumor malignancies or lymphoma, followed by Expansion period in patients with ovarian cancer in each treatment arm. Each arm of the study consists of a Dose Escalation Period in non-visceral lesions and a Dose Confirmation period in visceral lesions followed by a Dose Expansion Period in ovarian cancer.

Each dose level in the Dose Escalation Period will be conducted using a standard 3+3 study design in order to determine the safety and tolerability of each dose. For Arm A Dose Escalation, once a dose level has been cleared for safety, that dose level is open to enrollment of up to 9 additional patients who are willing and eligible to undergo tumor biopsy.

Once the expected MTD/RDE has been cleared in Dose Escalation for Arm A, Dose Escalation in Arm B will begin with mRNA-2416 at 1 dose level lower than the Arm A MTD/RDE according to the protocol Table 1.

For both arms, once the expected MTD/RDE has been cleared in Dose Escalation, Dose Confirmation of the MTD/RDE will be conducted in at least 3 patients with ovarian cancer with visceral lesions injectable

with ultrasound or computer tomography (CT) guidance. Dose Confirmation will be conducted in the same fashion as Dose Escalation.

For both arms, once the MTD and/or RDE has been determined in Dose Escalation/Confirmation, patients will be enrolled in the Expansion cohort in order to assess the preliminary anti-tumor activity of mRNA-2416 in ovarian cancer of epithelial origin.

Prior to enrollment, all patients will undergo screening to determine study eligibility. Arm A patients will receive mRNA-2416 for 6 cycles with 28 days in each cycle. Arm B patients will receive mRNA-2416 in combination with durvalumab for 6 cycles with 28 days in each cycle. Following completion of 6 cycles of combination dosing, patients may continue with durvalumab as a single-agent until disease progression, unacceptable toxicity, or 24 months of treatment (total), whichever is sooner. Patients completing study therapy with an overall tumor assessment of stable disease (SD) or better will be followed for efficacy for 6 months or until disease progression, whichever occurs first. Schedule of events can be found in the protocol.

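### SAP 5.1 leaves durvalumab stops after Cycle 6 out of the disposition table, so the optional single-agent phase has no rows and the two-year category cannot be filled

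*SAP*

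**What the plan says.** The disposition summary in SAP 5.1 gives, for durvalumab, "patients who completed durvalumab, patients who discontinued durvalumab, and the reasons for discontinuation of durvalumab". Completion is defined so: "Patients who completed 6 cycles of durvalumab treatment are considered for completion of durvalumab treatment". The next sentence deals with later stops: "Patients who discontinued durvalumab treatment after completing 6 cycles of durvalumab treatment are not considered for discontinuation of durvalumab treatment". The list of discontinuation reasons, just above these two sentences, includes "Completed 2 years of durvalumab treatment".

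The treatment being summarised has two parts. SAP 3.1 describes the first: "Arm B patients will receive mRNA-2416 in combination with durvalumab for 6 cycles with 28 days in each cycle". Protocol 8.3 describes the second, after those cycles: "patients may continue with durvalumab as a single-agent until disease progression, unacceptable toxicity, or 24 months of treatment (total), whichever is sooner". SAP 3.1 repeats this provision.

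Three other parts of the SAP bear on the point:
- SAP 7.3 counts single-agent continuation as part of the durvalumab treatment period when exposure is summarised.
- SAP 9.1 tabulates and lists the TEAEs that led to stopping durvalumab, with no limit by cycle.
- SAP 5.1 ends by promising listings of all disposition data.

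**The concern.** Exposure and adverse events are reported over the whole durvalumab period, but disposition is cut off at Cycle 6. A patient who stops single-agent durvalumab in Cycle 8 for toxicity or progression is tabulated as having completed durvalumab, with no reason shown, and cannot be told apart from one who reaches 24 months. The reason list and the completion rule also pull against each other, since one of the listed reasons needs a duration that the rule has already ruled out.

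At stake is how the Arm B disposition table reads. It describes durvalumab completion without saying that the completion is of the combination phase only. It also gives no tabulated account of why patients left the phase that can make up most of the maximum treatment time.

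**Working it through.** The plan states no figure to reproduce. The check is date arithmetic, followed by applying the SAP 5.1 rule to each type of patient.

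**Inputs.** Cycle length is 28 days and there are 6 combination cycles (SAP 3.1). The maximum is 24 months in total (Protocol 8.3). One month is 30.4375 days, the divisor used in SAP 6.2. Interruptions for reasons other than treatment-related AEs should end within 3 weeks unless discussed with the sponsor (Protocol 10.5).

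**Length of the phase without rows.**
- Six cycles: 6 × 28 = 168 days; 168 / 30.4375 = 5.5 months.
- Maximum: 24 × 30.4375 = 730.5 days; 730.5 / 28 = 26.1 cycles.
- Remainder: 730.5 − 168 = 562.5 days; 562.5 / 30.4375 = 18.5 months; 562.5 / 730.5 = 77% of the maximum duration.

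**Can the two-year reason be filled?** A patient would have to reach 24 months without having completed 6 cycles.
- With a 21-day delay in every cycle, six cycles take 6 × (28 + 21) = 294 days, or 9.7 months.
- Reaching 730.5 days on 5 cycles or fewer needs a mean interval of at least 730.5 / 5 = 146.1 days per cycle, against a planned 28.

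So nobody treated on anything close to the planned schedule can enter that row.

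**The rule applied to five illustrative patients.**

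| Patient | Durvalumab disposition row | Reason shown | In table of TEAEs that led to stopping durvalumab |
|---|---|---|---|
| Stops in Cycle 4, adverse event | Discontinued | Adverse event | Yes |
| Finishes 6 cycles, does not continue | Completed | None | No |
| Stops in Cycle 8, adverse event | Completed | None | Yes |
| Stops in Cycle 12, progression | Completed | None | No |
| Reaches 24 months | Completed | None | No |

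The last four patients share one row. The third is a completer in one table and a discontinuation in another.

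**The case against.** The strongest reply is that 6 cycles is the fixed course. Protocol 8.3 says that patients may continue, and Protocol 10.5 lists finishing 6 cycles with stable disease or better among the reasons for ending study therapy. Counting 6 cycles as completion is therefore a defensible choice, and it is stated openly. This stands for the combination phase. It does not explain why an optional phase that is delivered and counted as exposure has no disposition rows, nor why the reason list contains a category that only that phase could fill.

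Three stronger readings are tempting, and the documents support none of them.
- A reader might infer that the SAP suppresses every later stop. It does not. The disposition listings keep them, the AE tables keep those due to AEs, the exposure summary shows duration, and progression and death enter PFS with no cycle limit (SAP 8.3). What is lost is the tabulated count and reason, chiefly for progression, withdrawal of consent, investigator decision and other non-AE stops.
- A reader might take 77% as the share of discontinuations missed. It is a share of possible treatment time. The documents give no continuation rate. Expansion patients have platinum-resistant or refractory disease after at least 2 prior lines, so the number who reach Cycle 7 could be small.
- A reader might conclude that completion ought to mean 24 months. That would turn a patient who finishes 6 cycles and does not take up the optional phase into a discontinuation, which would be a new misclassification.

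**Conclusion.** The point holds for the disposition summary table. As written, SAP 5.1 gives no count of stops or reasons during single-agent durvalumab, a phase of up to 18.5 of the 24 months allowed, and it carries one reason category that is empty by construction. The counts of adverse-event stops in the disposition and AE tables will differ only if at least one patient stops durvalumab for a TEAE after Cycle 6. Whether that happens cannot be known from the documents.

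The conclusion assumes 28-day cycles with delays nowhere near a mean of 146 days per cycle. It also assumes that the SAP rule is programmed literally, which is reasonable because SAP section 1 says that the SAP prevails where it differs from the protocol. How many patients are affected is unknown. The table does not feed the response rate or the two-stage decision rules, so the primary endpoint, alpha and power are unaffected. This is a reporting flaw that should be corrected because it is internally contradictory and cheap to repair.

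**What to change.** Split the durvalumab part of the disposition table in two.
1. **Combination phase (6 cycles), all Arm B patients who received durvalumab:** completed, discontinued, ongoing, and reasons for discontinuation. Patients who finish 6 cycles and do not continue are completers here and are not discontinuations anywhere.
2. **Single-agent phase, only patients who enter it** (for example, those with at least one durvalumab dose after Cycle 6): completed, discontinued, ongoing, and reasons. Move the two-year category here as the definition of completion.

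Delete the sentence that removes later stops, or limit it to the first phase. Add a footnote that reconciles adverse-event stops across both phases with the table of TEAEs that led to stopping durvalumab.

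The cost is a SAP wording change, one derivation and a few extra rows, and the apparent completion rate becomes less favourable. New data collection looks unnecessary: Protocol 10.5 asks for the reason for stopping study therapy to be recorded on the eCRF, and SAP 7.3 already uses single-agent dosing records. The eCRF itself is not among the documents, so this should be confirmed. No treatment rule changes.
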